9.4.1.2 Secondary Efficacy Analysis

Secondary efficacy analyses will be performed using the randomized population. The FeNa, FeK, furosemide urinary and plasma concentration and the ratio of urinary sodium to urinary furosemide will be calculated at each time point over 4-hour urine/plasma collection after a bolus injection of 40 mg furosemide while receiving BMS-986231 or placebo. All data will be listed and tabulated. Graphical presentations may be provided.

A similar analysis as described in the primary efficacy analysis section will be conducted on the values derived at the 8-hour time point (8 hours after start of infusion).

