9.3.2 Secondary Endpoints

- FeNa, FeK, furosemide urinary and plasma concentration and ratio urinary sodium to urinary furosemide at 8 hours post-start infusion. Parameter values while patient is on BMS-986231 compared to placebo: absolute differences and % change from placebo.

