9.4.1.1 Primary Efficacy Analysis

All primary efficacy analyses will be performed using the treated (per protocol) population. Total amount of urine excreted over 4 hours after a bolus injection of 40 mg furosemide while receiving BMS-986231 or placebo will be summarized and analyzed. Volumes at each urinary collection

interval as well as total volume will be tabulated. Graphical presentations may be provided. All data will be listed.

A within patient analysis using a paired T-test will be performed to compare the volumes of urinary excretion and to test if there is a significantly different amount of urine secreted while receiving BMS-986231 versus placebo.

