9.4.3 Pharmacokinetic Analyses

Descriptive summaries will be presented for continuous variables using number of participants (n), mean, standard deviation (SD), median, minimum, and maximum. Descriptive summaries of PK data will additionally include geometric mean and coefficient of variation (CV%). Descriptive summaries for categorical variables will utilize counts (n) and percentages (%).

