3.0 Introduction

This Statistical Analysis Plan (SAP) describes the statistical methods that will be used during the analysis and reporting of data collected under Bristol-Myers Squibb Research and Development (BMS) Protocol CV013034.

This SAP should be read in conjunction with the study protocol and electronic case report form (eCRF). This version of the plan has been developed using the protocol dated 15-Apr-2019 (including all amendments up to this date) and the final eCRF(s) dated 22-Oct-2018.

An approved and signed SAP is a requirement for database lock.

This SAP only covers the results that will be processed by the PRA Early Development Services (EDS) Biostatistics Department.

PRA EDS will perform the efficacy, pharmacokinetic (PK), pharmacodynamic (PD), biomarker and safety and tolerability evaluations.

This SAP supersedes the statistical considerations identified in the protocol; where considerations are substantially different, they will be so identified. Any post-hoc or unplanned analyses, or significant changes from the planned analysis in this SAP performed to provide results for inclusion in the clinical study report (CSR) but not included in this SAP, will be clearly identified in the CSR. Changes to planned analyses do not require an updated SAP but should be discussed with the sponsor and included in the CSR if significant.

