7.0 Overview of Planned Analysis

7.1 Changes from Protocol

There are no changes from protocol

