15.3 Effect of BMS-986231 on furosemide concentration

Furosemide urinary and plasma concentrations and the ratio of urinary sodium to urinary furosemide will be calculated at each time point over 4-hour urine/plasma collection after a bolus injection of 40 mg furosemide while receiving BMS-986231 or placebo

Descriptive statistics (n, mean, SD, %CV, median, min, and max) will be used to summarize the absolute difference and the percent change from placebo of furosemide urine concentration, furosemide plasma concentration and the ratio of urinary sodium to urinary furosemide at 8 h by treatment.

Paired profiles of furosemide urine concentration, furosemide plasma concentration and the ratio of urinary sodium to urinary furosemide (4 h after furosemide dosing) will be provided for a visual representation of the data.

[REDACTED]

[REDACTED]

[REDACTED]

[REDACTED]

[REDACTED]

[REDACTED]

[REDACTED]

[REDACTED]

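### The protocol promises a paired t-test, with no log scale, on H8 furosemide levels and the sodium/furosemide ratio, and the SAP omits it undeclared; restore it on logs with a geometric mean ratio

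*Protocol*

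**What the plan says.** Protocol 9.3.2 names the secondary endpoints as "FeNa, FeK, furosemide urinary and plasma concentration and ratio urinary sodium to urinary furosemide at 8 hours post-start infusion" and sets the contrast as "Parameter values while patient is on BMS-986231 compared to placebo: absolute differences and % change from placebo". SAP 5.2.1 repeats both.

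For the analysis, Protocol 9.4.1.2 says: "A similar analysis as described in the primary efficacy analysis section will be conducted on the values derived at the 8-hour time point". The section it points to, Protocol 9.4.1.1, says: "A within patient analysis using a paired T-test will be performed to compare the volumes of urinary excretion". Neither mentions a transformation.

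SAP 15.3 covers furosemide concentrations and the sodium/furosemide ratio. It says that descriptive statistics "will be used to summarize the absolute difference and the percent change from placebo of furosemide urine concentration", plasma concentration and the ratio at 8 h, and it adds paired profile plots. It names no test and no confidence interval.

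On precedence, SAP 3.0 says: "This SAP supersedes the statistical considerations identified in the protocol; where considerations are substantially different, they will be so identified". SAP 7.1 says: "There are no changes from protocol".

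The log scale appears only descriptively. Protocol 9.4.3 adds a geometric mean to the PK summaries, and SAP 16.1.1 lists it for plasma furosemide concentrations.

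**The concern.** There are two linked problems.

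**The documents disagree on whether these endpoints are tested.** The protocol promises a within-patient test at H8. The SAP provides none and does not record the difference.

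**The scale suits these endpoints poorly.** A drug concentration and a ratio with a concentration in its denominator are positive and plausibly vary by multiples. Protocol 5.1 admits eGFR from 30 to 80, and H8 is 4 hours after the furosemide bolus, so differences in elimination have had time to spread the plasma values. If the effect of BMS-986231 is proportional, a patient's raw difference grows with that patient's own level, and the patients with the highest values carry most of the variance.

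These endpoints are meant to show whether BMS-986231 alters furosemide delivery or the sodium response to it. As things stand, that question gets either an inefficient test or no inference at all.

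**Working it through.** **1. The two documents side by side**

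| Endpoint | Protocol 9.4.1.2 | SAP text | SAP Appendix 4 |
|---|---|---|---|
| FeNa, FeK | similar to primary (paired t-test) | 15.2: paired t-test | Table 14.2.2.3, a statistical analysis table |
| Plasma and urinary furosemide, Na/furosemide ratio | similar to primary (paired t-test) | 15.3: descriptive statistics and plots | Table 14.2.4.1 (summary) and Figure 14.2.4.2 (plot) only |

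The only other statistical analysis table for efficacy is 14.2.1.4, for urine volume. The test on the furosemide endpoints is therefore absent from both the SAP text and its output list.

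**2. Which scale the protocol means.** The protocol does not name one. Raw is the natural reading: the contrast is an absolute difference and a % change, the primary test is on volumes, the PROC TTEST code in SAP 15.1 pairs the values with no log option, and no comparison in either document uses logs.

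**3. Size of the power loss.** There is no planned figure to reproduce. The only power statement (Protocol 9.1, SAP 6.1) is for urine output, and no variance, effect size or power is given for these endpoints.

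From the documents: 20 patients, hence 20 pairs (Protocol 9.1); two-sided 0.05 (SAP 8.4.3). Assumed: log-normal values, true ratio 1.30, within-patient CV 25% or 35%, between-patient CV 30% to 100%.

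Model: ln Y(placebo) = a + e1 and ln Y(BMS-986231) = a + ln 1.30 + e2, with a the patient's level and each variance equal to ln(1 + CV²).

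*On logs* the level a cancels. The SD of the difference is √2 × σW, and the noncentrality is ln 1.30 / SD × √20.
- CV 25%: σW = √ln 1.0625 = 0.246; SD = 0.348; 0.2624 / 0.348 × 4.472 = 3.37; power 0.89.
- CV 35%: σW = √ln 1.1225 = 0.340; SD = 0.481; 0.2624 / 0.481 × 4.472 = 2.44; power 0.64.

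*On the raw scale* the difference is exp(a) × (1.30 exp(e2) − exp(e1)). The level does not cancel, so power depends on the between-patient CV. Simulation with 100,000 trials per cell gives:

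| Between-patient CV | Raw vs log, within CV 25% | Raw vs log, within CV 35% | Loss (points) |
|---|---|---|---|
| 30% | 0.86 vs 0.89 | 0.58 vs 0.64 | 3-6 |
| 50% | 0.81 vs 0.89 | 0.54 vs 0.64 | 8-10 |
| 80% | 0.73 vs 0.89 | 0.46 vs 0.64 | 16-18 |
| 100% | 0.66 vs 0.89 | 0.41 vs 0.64 | 22-23 |

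With a true ratio of 1, the raw test rejects in 4.9% of trials at between-patient CV 30%, falling to 3.6% at 100%. The log test stays at about 5%.

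Concentration of influence: the two largest of the 20 squared deviations hold on average 47-49% of the raw sum of squares at between-patient CV 30% and 63-64% at 100%, against 41% on logs.

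**4. Could the between-patient CV reach 50%?** The documents cannot say. As an illustration for plasma only, let nothing vary but elimination half-life, log-normal with CV 30%, and take the concentration 4 h after the bolus as proportional to exp(−4 ln 2 / half-life). Assumed median half-lives of 1, 1.5, 2 and 3 h give concentration CVs of 72%, 49%, 38% and 26%. So 50% is reachable but not certain.

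**The case against.** **The SAP governs and contains no such test.** This is the strongest point, and it stands in part. A reader might infer that SAP 15.3 plans a raw-scale t-test on these endpoints and that its power is poor. The documents do not support that: the power figures describe the protocol's test, not a listed SAP output. Nor can one infer that the test was properly withdrawn, because SAP 3.0 says that substantial differences will be identified and SAP 7.1 declares none.

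**Raw scale is inferred.** True. The protocol says only that the analysis is similar, and its statistical section is a summary that leaves detail to the SAP.

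**The simulation favours logs.** True. The data are log-normal with multiplicative error, so the direction of the result is built in. Only its size is informative, and that depends on the assumed CVs.

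**The plan already has proportional summaries.** Partly. Percent change, its median and geometric means for plasma furosemide are planned, and a median percent change does describe a typical patient. But none of these comes with an interval for the treatment contrast. The mean percent change is also pulled upward: under the model above its expectation is 1.30 × (1 + CV²) − 1, which is 1.30 × 1.0625 − 1 = 38% at within-patient CV 25% and 1.30 × 1.1225 − 1 = 46% at 35%, for a true 30%.

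**Validity is not at risk.** Agreed. The raw test is, if anything, conservative.

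**Conclusion.** The concern holds as a mismatch between the documents together with an improvable choice of scale. The protocol promises a test without a log scale, the SAP omits it, and the omission is not declared. If the test is run on raw values, the loss of power under the stated assumptions is small at between-patient CV 30% (3-6 points), moderate at 50% (8-10) and large at 100% (22-23).

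A reader might conclude that power falls well below that of the log test as a matter of fact. That needs a between-patient CV of about 50% or more, which the documents neither give nor exclude. A reader might also suspect excess false positives; the calculation shows none. The endpoints are secondary, and nothing here bears on the scale of the urine-volume analysis. The case for change rests on a clear inconsistency and a cheap, standard remedy.

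**What to change.** - **Protocol 9.4.1.2 and SAP 15.3:** state that H8 plasma furosemide, urinary furosemide and the urinary sodium/furosemide ratio are compared by a paired t-test on log-transformed values and reported as the BMS-986231/placebo geometric mean ratio with 95% CI.
- **Protocol 9.3.2 and SAP 5.2.1:** add this ratio to the endpoint definitions. Keep the planned absolute and percent change summaries.
- **SAP Appendix 4:** add a statistical analysis table for these three endpoints.
- **Values below quantification:** state a rule for this comparison. SAP 16.1.1 sets such plasma values to missing for means only, and SAP 8.1.2 rules out imputation unless noted. Report how many pairs are affected.
- **SAP 7.1:** record any difference from the protocol that remains. If the sponsor prefers description only, that has to be declared here.

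Cost: a few sentences, a short piece of code, one extra table and the quantification rule; no new data. The downside is that the tested result is a ratio, not a difference in concentration units, although that difference is still tabulated.

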9.4.2 Safety Analyses

All safety analyses will be performed on the safety population (see Section 9.2). For safety analyses, all recorded AEs for each period will be listed and tabulated by system organ class, preferred term and treatment. Vital signs and clinical laboratory test results will be listed and summarized by treatment. Any significant physical examination findings, and clinical laboratory results will be listed. ECG readings will be evaluated by the investigator and abnormalities, if present, will be listed.

9.4.3 Pharmacokinetic Analyses

Descriptive summaries will be presented for continuous variables using number of participants (n), mean, standard deviation (SD), median, minimum, and maximum. Descriptive summaries of PK data will additionally include geometric mean and coefficient of variation (CV%). Descriptive summaries for categorical variables will utilize counts (n) and percentages (%).

9.4.4 Other Analyses

Results for other endpoints will be summarized descriptively. Model-based analyses may be performed, using models similar to the model for the primary endpoint.

9.4.5 Interim Analyses

Not applicable.

11 APPENDICES

APPENDIX 1 ABBREVIATIONS AND TRADEMARKS

Term	Definition
ACC	American College of Cardiology
ACEi	angiotensin-converting-enzyme inhibitor
ADHF	acute decompensated heart failure
ADME	absorption, distribution, metabolism, and excretion
AE	adverse event
AHA	American Heart Association
AHF	acute heart failure
ALT	alanine aminotransferase
ARB	angiotensin-receptor blockers
ARNI	angiotensin-receptor/neprilysin inhibitor
AST	aspartate aminotransferase
AVP	arginine-vasopressin system
BMS	Bristol-Myers Squibb
BNP	brain natriuretic peptide
bpm	beats per minute
BUN	blood urea nitrogen
CA125	cancer antigen 125
CI	cardiac index
CIs	confidence intervals
CONSORT	Consolidated Standards of Reporting Trials
CRF	case report form
CV	cardiovascular
CVA	cerebrovascular accident
D5W	5% dextrose in water
DBP	diastolic blood pressure
DILI	drug induced liver injury
DMC	Data Monitoring Committee
DNA	deoxyribonucleic acid
DTI	doppler tissue imaging
ECG	electrocardiogram
eCRF	electronic case report form
eGFR	estimated glomerular filtration rate
ESC	European Society of Cardiology
FDA	Food and Drug Administration
HCG	human chorionic gonadotropin
HF	heart failure
HFrEF	heart failure with reduced ejection fraction
HNO	Nitroxyl

Term	Definition
HR	heart rate
IB	investigator brochure
IEC	independent ethics committee
I(M)P	investigational (medicinal) product
IRB	institutional review board
ITT	intent to treat
IV	intravenous
K+	Potassium
LA	left atrium
LC-MS	liquid chromatography–mass spectrometry
LDH	lactate dehydrogenase
LV	left ventricle
LVEF	left ventricular ejection fraction
mARC	mitochondrial amidoxime-reducing component
MI	myocardial infarction
MMRM	mixed model repeated measures
MRA	mineralocorticoid receptor antagonists
MRI	magnetic resonance imaging
MUGA	multigated acquisition
MVO2	myocardial oxygen consumption
Na+	Sodium
NCV	nerve conduction velocities
N-GAL	gelatinase-associated lipocalin
NiCaS	noninvasive cardiac system
NO	nitric oxide
NT-pro BNP	N terminal- pro BNP
NYHA	New York Heart Association
PASP	pulmonary artery systolic pressure
PCWP	pulmonary capillary wedge pressure
PDE5	phosphodiesterase type 5
pH	potential of hydrogen
PK	pharmacokinetic
RA	right atrium
RAAS	renin-angiotensin-aldosterone system
RAP	right atrial pressure
RV	right ventricle
SAE	serious adverse event
SAP	statistical analysis plan
SBP	systolic blood pressure
sCD146	cluster of differentiation 146

Term	Definition
Scr	serum creatinine
SD	standard deviation
SERCA	sarcoplasmic reticulum calcium adenosine triphosphatase
SGOT	serum glutamic-oxaloacetic transaminase
SGPT	serum glutamic pyruvic transaminase
SNS	sympathetic nervous system
SUSAR	suspected, unexpected serious adverse reaction
TAPSE	tricuspid annular plane systolic excursion
TIA	transient ischemic attack
TR	tricuspid regurgitation
uACR	urine albumin-to-creatinine ratio
ULN	upper limit of normal
WOCBP	women of child bearing potential

APPENDIX 2 STUDY GOVERNANCE CONSIDERATIONS

The term 'Participant' is used in the protocol to refer to a person who has consented to participate in the clinical research study. The term 'Subject' used in the eCRF is intended to refer to a person (Participant) who has consented to participate in the clinical research study.

REGULATORY AND ETHICAL CONSIDERATIONS GOOD CLINICAL PRACTICE

This study will be conducted in accordance with:

- Good Clinical Practice (GCP)
- as defined by the International Council on Harmonisation (ICH)
- in accordance with the ethical principles underlying European Union Directive 2001/20/EC
- United States Code of Federal Regulations, Title 21, Part 50 (21CFR50)
- applicable local requirements

The study will be conducted in compliance with the protocol. The protocol and any amendments and the participant informed consent will receive approval/favorable opinion by Institutional Review Board/Independent Ethics Committee (IRB/IEC), and regulatory authorities according to applicable local regulations prior to initiation of the study.

All potential serious breaches must be reported to Sponsor or designee immediately. A serious breach is a breach of the conditions and principles of GCP in connection with the study or the protocol, which is likely to affect, to a significant degree, the safety or physical or mental integrity of the subjects of the study or the scientific value of the study.

Personnel involved in conducting this study will be qualified by education, training, and experience to perform their respective tasks.

This study will not use the services of study personnel where sanctions have been invoked or where there has been scientific misconduct or fraud (e.g., loss of medical licensure, debarment).

INSTITUTIONAL REVIEW BOARD/INDEPENDENT ETHICS COMMITTEE

Before study initiation, the investigator must have written and dated approval/favorable opinion from the IRB/IEC for the protocol, consent form, participant recruitment materials (e.g., advertisements), and any other written information to be provided to subjects. The investigator or BMS should also provide the IRB/IEC with a copy of the Investigator Brochure or product labeling information to be provided to subjects and any updates.

The investigator, Sponsor or designee should provide the IRB/IEC with reports, updates and other information (e.g., expedited safety reports, amendments, and administrative letters) according to regulatory requirements or institution procedures.

COMPLIANCE WITH THE PROTOCOL AND PROTOCOL REVISIONS

The investigator should not implement any deviation or change to the protocol without prior review and documented approval/favorable opinion of an amendment from the IRB/IEC (and if applicable, also by local health authority) except where necessary to eliminate an immediate hazard(s) to study subjects.

If a deviation or change to a protocol is implemented to eliminate an immediate hazard(s) prior to obtaining relevant approval/favorable opinion(s) the deviation or change will be submitted, as soon as possible to:

- IRB/IEC for
- Regulatory Authority(ies), if applicable by local regulations (per national requirements)

Documentation of approval/favorable opinion signed by the chairperson or designee of the IRB(s)/IEC(s) and if applicable, also by local health authority must be sent to BMS.

If an amendment substantially alters the study design or increases the potential risk to the participant: (1) the consent form must be revised and submitted to the IRB(s)/IEC(s) for review and approval/favorable opinion; (2) the revised form must be used to obtain consent from subjects currently enrolled in the study if they are affected by the amendment; and (3) the new form must be used to obtain consent from new subjects prior to enrollment.

If the revision is done via an administrative letter, investigators must inform their IRB(s)/IEC(s).

FINANCIAL DISCLOSURE

Investigators and sub-Investigators will provide the Sponsor with sufficient, accurate financial information in accordance with local regulations to allow the Sponsor to submit complete and accurate financial certification or disclosure statements to the appropriate health authorities. Investigators are responsible for providing information on financial interests during the course of the study and for 1 year after completion of the study.

INFORMED CONSENT PROCESS

Investigators must ensure that subjects are clearly and fully informed about the purpose, potential risks, and other critical issues regarding clinical studies in which they volunteer to participate.

In situations where consent cannot be given to subjects, their legally acceptable representatives (as per country guidelines) are clearly and fully informed about the purpose, potential risks, and other critical issues regarding clinical studies in which the participant volunteers to participate.

Sponsor or designee will provide the investigator with an appropriate (i.e., Global or Local) sample informed consent form which will include all elements required by ICH, GCP and applicable regulatory requirements. The sample informed consent form will adhere to the ethical principles that have their origin in the Declaration of Helsinki.

Investigators must:

- Provide a copy of the consent form and written information about the study in the language in which the participant is most proficient prior to clinical study participation. The language must be non-technical and easily understood.
- Allow time necessary for participant or participant's legally acceptable representative to inquire about the details of the study.
- Obtain an informed consent signed and personally dated by the participant or the participant's legally acceptable representative and by the person who conducted the informed consent discussion.
- Obtain the IRB/IEC's written approval/favorable opinion of the written informed consent form and any other information to be provided to the subjects, prior to the beginning of the study, and after any revisions are completed for new information.

If informed consent is initially given by a participant's legally acceptable representative or legal guardian, and the participant subsequently becomes capable of making and communicating his or her informed consent during the study, consent must additionally be obtained from the participant.

Revise the informed consent whenever important new information becomes available that is relevant to the participant's consent. The investigator, or a person designated by the investigator, should fully inform the participant or the participant's legally acceptable representative or legal guardian, of all pertinent aspects of the study and of any new information relevant to the participant's willingness to continue participation in the study. This communication should be documented.

The confidentiality of records that could identify subjects must be protected, respecting the privacy and confidentiality rules applicable to regulatory requirements, the subjects' signed ICF and, in the US, the subjects' signed HIPAA Authorization.

The consent form must also include a statement that BMS and regulatory authorities have direct access to participant records.

The rights, safety, and well-being of the study subjects are the most important considerations and should prevail over interests of science and society.

SOURCE DOCUMENTS

The investigator is responsible for ensuring that the source data are accurate, legible, contemporaneous, original and attributable, whether the data are hand-written on paper or entered electronically. If source data are created (first entered), modified, maintained, archived, retrieved, or transmitted electronically via computerized systems (and/or any other kind of electronic devices) as part of regulated clinical trial activities, such systems must be compliant with all applicable laws and regulations governing use of electronic records and/or electronic signatures. Such systems may include, but are not limited to, electronic medical/health records (EMRs/EHRs), AE tracking/reporting, protocol required assessments, and/or drug accountability records).

When paper records from such systems are used in place of electronic format to perform regulated activities, such paper records should be certified copies. A certified copy consists of a copy of

original information that has been verified, as indicated by a dated signature, as an exact copy having all of the same attributes and information as the original.

STUDY TREATMENT RECORDS

Records for study treatments (whether supplied by BMS, its vendors, or the site) must substantiate study treatment integrity and traceability from receipt, preparation, administration, and through destruction or return. Records must be made available for review at the request of BMS/designee or a Health Authority.

If	Then
Supplied by BMS (or its vendors):	
Records or logs must comply with applicable regulations and guidelines and should include:
 
• amount received and placed in storage area• amount currently in storage area• label identification number or batch number• amount dispensed to and returned by each participant, including unique participant identifiers• amount transferred to another area/site for dispensing or storage• non-study disposition (e.g., lost, wasted)• amount destroyed at study site, if applicable• amount returned to BMS• retain samples for bioavailability/bioequivalence, if applicable• dates and initials of person responsible for Investigational Product dispensing/accountability, as per the Delegation of Authority Form.
Sourced by site, and not supplied by BMS or its vendors (examples include IP sourced from the sites stock or commercial supply, or a specialty pharmacy)	The investigator or designee accepts responsibility for documenting traceability and study drug integrity in accordance with requirements applicable under law and the SOPs/standards of the sourcing pharmacy.

	
These records should include:
 
• label identification number or batch number• amount dispensed to and returned by each participant, including unique participant identifiers• dates and initials of person responsible for Investigational Product dispensing/accountability, as per the Delegation of Authority Form.
--	--

BMS or designee will provide forms to facilitate inventory control if the investigational site does not have an established system that meets these requirements.

CASE REPORT FORMS

An investigator is required to prepare and maintain adequate and accurate case histories designed to record all observations and other data pertinent to the investigation on each individual treated or entered as a control in the investigation. Data that are derived from source documents and reported on the CRF must be consistent with the source documents or the discrepancies must be explained. Additional clinical information may be collected and analyzed in an effort to enhance understanding of product safety. CRFs may be requested for AEs and/or laboratory abnormalities that are reported or identified during the course of the study.

For sites using the Sponsor or designee electronic data capture tool, electronic CRFs will be prepared for all data collection fields except for fields specific to SAEs and pregnancy, which will be collected and reported on the paper Safety Report Form and paper Pregnancy Surveillance Form, respectively. Spaces may be left blank only in those circumstances permitted by study-specific CRF, Safety Report Form, or Pregnancy Surveillance Form completion guidelines provided by PRA.

The confidentiality of records that could identify subjects must be protected, respecting the privacy and confidentiality rules in accordance with the applicable regulatory requirement(s).

The investigator will maintain a signature sheet to document signatures and initials of all persons authorized to make entries and/or corrections on CRFs.

The completed CRF, SAE and/or pregnancy forms, must be promptly reviewed, signed, and dated by the investigator or qualified physician who is a sub-investigator and who is delegated this task on the Delegation of Authority Form. Sub-investigators in Japan may not be delegated the CRF approval task. For electronic CRFs, review and approval/signature is completed electronically through the BMS electronic data capture tool. The investigator must retain a copy of the CRFs including records of the changes and corrections. Each individual electronically signing electronic CRFs must meet Sponsor or designee training requirements and must only access the BMS electronic data capture tool using the unique user account provided by Sponsor or designee. User accounts are not to be shared or reassigned to other individuals.

MONITORING

Sponsor or designee representatives will review data centrally to identify potential issues to determine a schedule of on-site visits for targeted review of study records.

Representatives of BMS must be allowed to visit all study site locations periodically to assess the data quality and study integrity. On site they will review study records and directly compare them with source documents, discuss the conduct of the study with the investigator, and verify that the facilities remain acceptable. Certain CRF pages and/or electronic files may serve as the source documents:

In addition, the study may be evaluated by Sponsor or designee internal auditors and government inspectors who must be allowed access to CRFs, source documents, other study files, and study facilities. BMS audit reports will be kept confidential.

The investigator must notify BMS promptly of any inspections scheduled by regulatory authorities, and promptly forward copies of inspection reports to Sponsor or designee.

RECORDS RETENTION

The investigator (or head of the study site in Japan) must retain all study records and source documents for the maximum period required by applicable regulations and guidelines, or institution procedures, or for the period specified by BMS or designee, whichever is longer. The investigator (or head of the study site in Japan) must contact BMS prior to destroying any records associated with the study.

BMS or designee will notify the investigator (or head of the study site in Japan) when the study records are no longer needed.

If the investigator withdraws from the study (e.g., relocation, retirement), the records shall be transferred to a mutually agreed upon designee (e.g., another investigator, study site, IRB). Notice of such transfer will be given in writing to BMS or designee.

RETURN OF STUDY TREATMENT

For this study, study treatments (those supplied by BMS, a vendor or sourced by the investigator) such as partially used study treatment containers, vials and syringes may be destroyed on site.

If..	Then
Study treatments supplied by BMS (including its vendors)	
Any unused study treatments supplied by BMS can only be destroyed after being inspected and reconciled by the responsible Study Monitor unless study treatments containers must be immediately destroyed as required for safety, or to meet local regulations (e.g., cytotoxics or biologics).
 
If study treatments will be returned, the return will be arranged by the responsible Study Monitor.

Study treatments sourced by site, not supplied by BMS (or its vendors) (examples include study treatments sourced from the sites stock or commercial supply, or a specialty pharmacy)	
It is the investigator's or designee's responsibility to dispose of all containers according to the institutional guidelines and procedures.

It is the investigator's or designee's responsibility to arrange for disposal, provided that procedures for proper disposal have been established according to applicable federal, state, local, and institutional guidelines and procedures, and provided that appropriate records of disposal are kept.

The following minimal standards must be met:

- On-site disposal practices must not expose humans to risks from the drug.
- On-site disposal practices and procedures are in agreement with applicable laws and regulations, including any special requirements for controlled or hazardous substances.
- Written procedures for on-site disposal are available and followed. The procedures must be filed with the site's SOPs and a copy provided to BMS upon request.
- Records are maintained that allow for traceability of each container, including the date disposed of, quantity disposed, and identification of the person disposing the containers. The method of disposal, i.e., incinerator, licensed sanitary landfill, or licensed waste disposal vendor must be documented.
- Accountability and disposal records are complete, up-to-date, and available for the Monitor to review throughout the clinical trial period.

It is the investigator's or designee's responsibility to arrange for disposal of all empty containers. If conditions for destruction cannot be met the responsible Study Monitor will make arrangements for

return of study treatments provided by BMS (or its vendors). Destruction of non- study treatments sourced by the site, not supplied by BMS, is solely the responsibility of the investigator or designee.

For this study, study treatments (those supplied by BMS or its vendors) such as full or partially used study treatment containers, vials, syringes cannot be destroyed on site.

It is however, the investigator's or designee's responsibility to arrange for disposal of all empty study treatment containers, provided that procedures for proper disposal have been established according to applicable federal, state, local, and institutional guidelines and procedures, and provided that appropriate records of disposal are kept. The return of full or partially used study treatments supplied by BMS or its vendors will be arranged by the responsible Study Monitor.

CLINICAL STUDY REPORT AND PUBLICATIONS

For this protocol, the Signatory Investigator will be selected as appropriate based on the following criteria:

- External Principal Investigator designated at protocol development
- National Coordinating Investigator
- Study Steering Committee chair or their designee
- Participant recruitment (e.g., among the top quartile of enrollers)
- Involvement in trial design
- Regional representation (e.g., among top quartile of enrollers from a specified region or country)
- Other criteria (as determined by the study team)

The data collected during this study are confidential and proprietary to Sponsor or designee. Any publications or abstracts arising from this study must adhere to the publication requirements set forth in the clinical trial agreement (CTA) governing [Study site or investigator] participation in the study. These requirements include, but are not limited to, submitting proposed publications to Sponsor or designee at the earliest practicable time prior to submission or presentation and otherwise within the time period set forth in the CTA.

APPENDIX 3 ADVERSE EVENTS AND SERIOUS ADVERSE EVENTS: DEFINITIONS AND PROCEDURES FOR RECORDING, EVALUATING, FOLLOW-UP AND REPORTING

ADVERSE EVENTS

Adverse Event Definition:
An Adverse Event (AE) is defined as any new untoward medical occurrence or worsening of a preexisting medical condition in a clinical investigation participant administered study treatment and that does not necessarily have a causal relationship with this treatment.
An AE can therefore be any unfavorable and unintended sign (such as an abnormal laboratory finding), symptom, or disease temporally associated with the use of study drug, whether or not considered related to the study drug.
Events Meeting the AE Definition

• Any abnormal laboratory test results (hematology, clinical chemistry, or urinalysis) or results from other safety assessments (eg, ECG, radiological scans, vital signs measurements), including those that worsen from baseline, considered clinically significant in the medical and scientific judgment of the investigator. Note that abnormal lab tests or other safety assessments should only be reported as AEs if the final diagnosis is not available. Once the final diagnosis is known, the reported term should be updated to be the diagnosis.• Exacerbation of a chronic or intermittent pre-existing condition including either an increase in frequency and/or intensity of the condition.• New conditions detected or diagnosed after study intervention administration even though it may have been present before the start of the study.• Signs, symptoms, or the clinical sequelae of a suspected drug-drug interaction.• Signs, symptoms, or the clinical sequelae of a suspected overdose of either study intervention or a concomitant medication. Overdose, as a verbatim term (as reported by the investigator), should not be reported as an AE/SAE unless it is an intentional overdose taken with possible suicidal/self-harming intent. Such overdoses should be reported regardless of sequelae and should specify “intentional overdose” as the verbatim term.

Events NOT Meeting the AE Definition

- Medical or surgical procedure (eg, endoscopy, appendectomy): the condition that leads to the procedure is the AE.
- Situations in which an untoward medical occurrence did not occur (social and/or convenience admission to a hospital).

DEFINITION OF SAE

If an event is not an AE per definition above, then it cannot be an SAE even if serious conditions are met.

SERIOUS ADVERSE EVENTS

Serious Adverse Event Definition: Any untoward medical occurrence that, at any dose:	
Results in death	
Is life-threatening (defined as an event in which the participant was at risk of death at the time of the event; it does not refer to an event which hypothetically might have caused death if it were more severe)	
Requires inpatient hospitalization or causes prolongation of existing hospitalization (see NOTE below)	
